Tranexamic acid to Reduce Infection after Gastrointestinal Surgery: the TRIGS Trial

2. Trial registration

Prospectively registered (ClinicalTrials.gov identifier NCT04192435)

3. SAP version

Version: 1.0 Date: 07/11/2025

4. Protocol Version

This document has been written based on information contained in the TRIGS study protocol Version 1.4 dated 30 June 2022.

5. SAP Revisions

This SAP provides additional details and clarifies analysis approaches outlined in the TRIGS study protocol.

6. Names and affiliations

Document prepared by [name], Monash University; and [name], Alfred Hospital

[name]

Signatures:

Signature of senior statistician responsible ([name]):

Date: 13/11/2025

Date: 13/11/2025

Signature of chief investigator ([name]):

3

7. Brief background and rationale

Refer to the protocol for a detailed background to this trial, version 1.4, dated 30 June 2022.

8. Objectives

Research hypothesis:

We hypothesise that among adult patients schedule for elective or semi-elective open or lap-assisted gastrointestinal surgery (oesophageal, gastric, hepatobiliary, pancreatic, colorectal) with one or more risk factors for complications that a bolus of study drug (0.15 ml/kg TxA 15mg/kg before surgical incision, and then infusion at 0.05 ml/kg/h until end of surgery) will reduce the incidence of surgical site infection compared to matched placebo.

Study objective:

Primary objective: To determine whether TxA, compared to matched placebo, decreases the risk of surgical site infection

SAP version: Version: 1.0 Date: 13/11/2025

Section 3: Trial Methods

9. Trial design

International, multicentre, pragmatic, double-blind, placebo-controlled randomised clinical trial.

10. Randomisation

Patients will be randomly assigned using permuted blocks of sizes 6 to 12 from a computer-generated list to either receive IV TxA or placebo on the day of surgery, but after confirmation of scheduling. Random assignment will be done using a computer-generated code, accessed via a web-based service. Group assignment will be stratified by site and diabetes status.

11. Sample size

In our recently completed RELIEF trial, in which we enrolled near-identical patients to that proposed in this trial, the pooled incidence of SSI was 14% (consistent with global data²) and red cell transfusions were used in 12% of patients. An incidence of SSI of up to 25% has been reported in other at-risk major gastrointestinal surgical cohorts.43, 44 Assuming an incidence of 12%, and using a type I error of 0.05, we require 1,484 per group in order to have 90% power to detect a 30% reduction in SSI to 8.4% (i.e. relative risk 0.7). Were the control group incidence 14%, this sample size provides 94% power to detect a 30% reduction to 9.8%. We plan to enrol 3,300 patients. This will also provide ≥90% power to detect a 30% reduction in blood transfusions.

Assuming 30% of patients are diabetic and an incidence of SSI in non-diabetic patients in the placebo arm of 10%, this sample size provides \approx 70% power to detect a difference in treatment relative risks of 0.55 in non-diabetic patients and 0.94 in diabetic patients on the multiplicative relative risks scale.45

12. Framework

This trial uses a superiority hypothesis testing framework between groups for the primary outcomes. Results will be reported in accordance with the CONSORT 2025 statement.

13. Statistical interim analyses and stopping guidance

Interim analyses will consider the defined study and safety endpoints after enrolment of 50% and 75% of patients, adjusted according to the O'Brien and Fleming method. Results will be made available to the DSMC, consisting of experts in the fields of surgery, infectious diseases and anaesthesia, and an independent statistician (Chair: [name], UK).

Section 4: Statistical Principles

14. Level of statistical significance

All applicable statistical tests will be 2-sided and will be performed using a 5% significance level.

15. Description of any planned adjustment for multiplicity, and if so, including how the type 1 error is to be controlled

No adjustment for multiplicity is planned.

16. Confidence intervals to be reported

All confidence intervals will be two-sided 95% confidence intervals.

17. Analysis Populations and Estimand

Except where stated otherwise, all analyses will be conducted under the principle of modified intention-to-treat, whereby all participants are included in their randomised groups, but only those participants who underwent a surgical incision will be included in the analysis.

The primary estimand of interest is described in the table below.

Objective: To determine whether TxA, compared to matched placebo, decreases the risk of surgical site infection.

Estimand: Relative risk of incidence of any surgical site infection (superficial, deep, or organ space) among adult patients undergoing elective or semi-elective open or lap-assisted gastrointestinal surgery (oesophageal, gastric, hepatobiliary, pancreatic, colorectal) with one or more risk factors for complications assigned to receive treatment, relative to assignment to receive a matched placebo.

Treatment: 0.15 ml/kg TxA 15mg/kg before surgical incision, and then infusion at 0.05 ml/kg/h until end of surgery

surgery			
ESTIMAND	ANALYSIS		
Target population : adult patients undergoing elective or semi-elective open or lap-assisted gastrointestinal surgery (oesophageal, gastric, hepatobiliary, pancreatic, colorectal) with one or more risk factors	Analysis set: All randomized participants who undergo surgery. Patients assigned to receive TxA through randomization will be the treatment group, patients assigned to receive the placebo the comparator group.		
Variable: SSI (superficial, deep, and organ space), as defined by the US Centers for Disease Control (CDC), 14 up to 30 days after surgery. This includes all five separate categories of SSI, (Superficial Incisional Primary, Superficial Incisional Secondary, Deep Incisional Primary, Deep Incisional Secondary and Organ Space infection).	Outcome measure: Surgical site infection. Trial patients will be seen and have their medical records (and any cultures done) reviewed on a daily basis whilst in hospital, and a formal wound inspection done on Day 3 and day of discharge, plus a 30-day medical record/pathology review done. Any late (>30 postoperative days) notifications of SSI up to 90 days after surgery will be included in the outcome.		
Handling of intercurrent events: - Treatment as randomized not received:	Handling of missing data : Multiple imputation will be applied if >5% of the participants in the analysis		
patients included in their randomized groups (treatment policy strategy) - Death prior to identification of SSI within the relevant window: if a patient dies prior to the identification of an SSI, their outcome will be "no SSI" ("while alive" strategy)	set have a missing primary outcome. Results of a complete case analysis will also be provided. Supplementary analysis: The analysis of the primary outcome will be repeated in As-treated and Per Protocol analysis sets.		

The relative risk

will

Population-level summary measure: Relative risk | Analysis approach:

of SSI if treated with TxA compared with no TxA.	estimated using a log-binomial model adjusted for the
	stratification variable of diabetes, with random effects
	for the stratifying variable of site.

Section 5: Trial Population

18. Screening Data

Screening data will be collected and a CONSORT flow diagram will be used to summarise this data.

19. Eligibility

Trial inclusion criteria are described in the trial protocol. Reasons for exclusion will be summarised in the CONSORT flow diagram.

20. Recruitment

A CONSORT flow diagram will be used to describe the number of people consented to participate, randomised, allocated to each treatment group, those lost to follow up (including reasons) and analysed.

21. Withdrawal/follow-up

All participants who are enrolled and randomly assigned to a group, and undergo surgery, must be followed for the duration of the study (unless they withdraw consent) even if they are withdrawn from the active phase of the trial. Losses to follow-up (including reasons) will be summarised in the CONSORT flow diagram by treatment group.

22. Baseline descriptive measures

Baseline characteristics will be summarised as appropriate (means and standard deviations for continuous variables that appear to be distributed approximately symmetrically, medians and interquartile ranges for other continuous variables, counts and percentages for categorical variables). Tests of statistical significance will not be undertaken for comparing baseline characteristics of treatment groups; rather the clinical importance of any imbalance will be noted.

An appendix table will provide summaries of baseline characteristics and compare these characteristics between two groups: those patients for whom the primary outcome was provided, and those patients for whom the primary outcome is missing. T-tests will be used to compare continuous characteristics between these groups, and chi-squared tests will be used to compare categorical characteristics, and this will help to determine which variables should be included as auxiliary variables in models for the imputation of the outcome.

Section 6: Analysis

23. Outcome definitions

Name	Description	Scale	Outcome definition
Primary Outcome			
Surgical site infection	Binary outcome: any incidence of surgical site infection (superficial, deep, and organ space)	Binary variable: 0 = No surgical site infection 1= surgical site infection	SSI (superficial, deep, and organ space), as defined by the US Centers for Disease Control (CDC), 14 up to 30 days after surgery – see Table. This includes all five separate categories of SSI, (Superficial Incisional Primary, Superficial Incisional Primary, Deep Incisional Primary, Deep Incisional Primary, Deep Incisional Secondary and Organ Space infection). Trial patients will be seen and have their medical records (and any cultures done) reviewed on a daily basis whilst in hospital, and a formal wound inspection done on Day 3 and day of discharge, plus a 30-day medical record/pathology review done. Any late (>30 postoperative days) notifications of SSI up to 90 days after surgery will be included in our primary endpoint
Secondary Outcomes			enapoint
Any red cell transfusion	Binary outcome: any red cell transfusion	Binary variable: 0 = no red call transfusion; 1 = any red cell transfusion	Any red cell transfusion up to hospital discharge
Volume of red cell transfusion (units)	Continuous outcome: total no. of units transfused	Continuous variable with lower limit of 0	Total no. of red cell units transfused up to hospital discharge
Sepsis	Binary outcome: any incidence of sepsis	Binary variable 0 = no sepsis; 1 = sepsis	Definition of sepsis using CDC-guided definition occurring on or after day 3 but during initial hospitalisation
Pneumonia	Binary outcome: any incidence of pneumonia	Binary variable 0 = no pneumonia; 1 = pneumonia	Definition of pneumonia using CDC-guided definition occurring on or after day 3 but during initial hospitalisation
Other infection	Binary outcome: any incidence of urinary tract (UTI) or "other" infection	Binary variable 0 = no other infection; 1 = UTI or other infection	Any clinical documentation of UTI or other infection
Anastomotic leak	Binary outcome: any incidence of anastomotic leak of any grade	Binary variable 0 = no anastomotic leak; 1 = any anastomotic leak	A defect of the intestinal wall at the anastomotic site (including suture and staple lines of neorectal reservoirs) leading to a communication between the intra- an extra luminal compartments. 1. Grade A - anastomotic

SAP version: Version: 1.0 Date: 13/11/2025

Trial: Tranexamic acid to Reduce Infection after Gastrointestinal Surgery: the TRIGS Trial

			leakage results in no change in patients' management 2. Grade B - leakage requires active therapeutic intervention but is manageable without relaparotomy 3. Grade C - anastomotic
			leakage requires re- laparotomy
Peak-C reactive protein (CRP)	Continuous outcome: concentration of CRP	Continuous outcome with lower limit of 0.	Concentration of CRP on postoperative day 3
Days alive and at home up to 30 days after surgery	Number of days at home up to 30 days after surgery	Continuous outcome with range of 0 to 30	Number of days that a patient is alive and at home up to 30 days after surgery.
Postoperative diagnosis of COVID-19	Binary outcome: any diagnosis of COVID-19 in the 30 days after surgery	Binary variable 0 = no diagnosis of COVID-19; 1 = any diagnosis of COVID-19	Any diagnosis of COVID-19 in the 30-day study period
Safety Outcomes			
Thromboembolism	Binary outcome: any incidence of DVT or PE	Binary variable 0 = no no thromboembolism; 1 = thromboembolism	A clinical diagnosis of DVT or PE up to 30 days after surgery
Seizures	Binary outcome: any incidence of seizure	Binary variable 0 = no seizure; 1 = seizure	A seizure up to 30 days after surgery
Cardiovascular events (MI, stroke)	Binary outcome: any incidence of clinical MI or stroke	Binary variable 0 = no cardiovascular event; 1 = cardiovascular event	A clinical diagnosis of myocardial infarction or stroke up to 30 days after surgery
Anaphylactoid reactions	Binary outcome: any incidence of anaphylactoid reaction post-IV study drug delivery	Binary variable 0 = no anaphylactoid reaction; 1 = anaphylactoid reaction	An anaphylactoid reaction following study drug administration
Blood transfusion reactions	Binary outcome: any incidence of transfusion reaction	Binary variable 0 = no transfusion reaction; 1 = transfusion reaction	Any blood transfusion reaction following any blood product transfusion

24. Analysis methods

Analysis of primary outcome, and binary secondary/safety outcomes:

For the primary analysis of binary outcomes, we will use log-binomial models adjusting for the stratification variable of diabetes, with random effects for the stratifying variable of site. If that model fails to converge, a log-binomial model with the same link function and adjusting for the stratification variable of diabetes but with cluster-robust standard errors instead of random effects for site. Results will be expressed as risk ratios with 95% confidence intervals.

For analyses based on multiply imputed datasets: if a model fails to converge for more than one quarter of imputed datasets, the model with cluster-robust standard errors will instead be fit.

Days at home up to 30 days after surgery

DAH30 will be compared between groups using median regression adjusting for the stratification variable of diabetes, with cluster robust standard errors for site. DAH-30 is calculated using mortality and hospitalisation data from the date of the index surgery (= Day 0). For example, if a patient died on day 2 after their surgery whilst still an inpatient, they would be assigned zero (0) days at home; if a patient was discharged from hospital on Day 6 after surgery but was subsequently re-admitted for 4 days before their second hospital discharge, then they would be assigned a DAH-30 value of 20. If a patient has complications and spends 16 days in hospital, and then is transferred to a nursing facility for rehabilitation, and spend 24 days there before finally being discharged to their own home, they would be assigned a DAH-30 value of zero (0), even though 30-16-

24 = -10 because the minimum value of DAH-30 should be zero. If a patient dies within 30 days of surgery, irrespective of whether they have spent some time at home, DAH-30 will be scored as zero (0).

In addition to presenting a difference in medians between groups with respect to DAH-30, a difference in lower quartiles (i.e. 25th percentiles) will be presented.

Peak C Reactive protein and volume of red blood cell transfusion

These outcomes will be compared between groups using mixed effects linear regression models adjusting for the stratification variable of diabetes, with random effects for the stratifying variable of site.

25. Statistical Methods – adjustment for covariates

Supplementary analyses for the primary outcome and the secondary outcome of any red cell transfusion will adjust for any prognostic variables imbalanced at baseline.

For the primary outcome, variables with apparent imbalance out of the following list will be adjusted for:

- Patient age
- ASA physical status
- Diabetes
- Current smoker
- Oral steroid
- Open surgery

For the outcome of any red cell transfusion, variables with apparent imbalance out of the following list will be adjusted for:

- Patient age
- ASA physical status
- Body mass index (weight/height²)
- Chronic renal disease
- Aspirin
- Preoperative haemoglobin
- Open surgery

26. Statistical Methods – subgroup analyses

Subgroup analyses of the primary outcome and any red cell transfusion will be conducted for the following subgroups:

- i) Age strata (\leq 60 yr; 61–70 yr;71–75 yr;>75 yr);
- ii) Patient sex;
- iii) BMI strata (≤ 18.5 ; $\geq 18.5-25.0$; $\geq 25.0-30.0$; $\geq 30.0-35.0$; ≥ 35.0);
- iv) ASA physical status
- v) Diabetes status (i.e. the stratification variable);
- vi) Country;
- vii) Type of GI surgery;
- viii) Duration of surgery (approximate quartiles)

Models for these analyses will be as described in Section 27 for the primary analysis, including terms for the subgroup indicator and interactions between the subgroup and randomised group. Treatment effects in each subgroup will be reported.

27. Missing data reporting and assumptions/statistical methods to handle missing data

Multiple imputation of outcomes will be undertaken if the proportion of missingness of the primary outcome

is >5%.

Missing baseline characteristics will be imputed using single mean imputation. Baseline characteristics of participants who did and did not provide the primary outcome will be compared, and will be used to inform multiple imputation models. T-tests or Wilcoxon rank-sum tests will be used to compare continuous characteristics (depending on whether these had approximately symmetric distributions or not); chi-squared tests will compare categorical characteristics between participants with and without the primary outcome.

Missing outcome values will be imputed separately by treatment group. Imputation models will include treatment group, diabetes status, and baseline characteristics that appear to be different between participants who provided complete follow up data and participants who did not. Imputation models for continuous outcomes will also include terms for site. Imputation models for binary outcomes will not include terms for site due to the possibility of perfect prediction in small sites.

Initially, imputation via chained equations will be attempted for outcomes, with separate imputation for each outcome if this imputation fails. Binary outcomes will be imputed using logistic regression models, and continuous outcomes imputed via with predictive mean matching from the 5 nearest neighbours. Imputed datasets will be compared to complete data using density plots for continuous outcomes and plots of proportions for binary outcomes.

28. Additional Analyses

As-treated and per protocol analyses of the primary outcome and any red cell transfusion will also be conducted. As noted in the E9(R1) addendum, these additional analyses may be subject to severe bias and may not correspond to a relevant estimand.

Data collected prior to the trial re-start (the "contamination dataset") will also be considered. A table summarizing the baseline characteristics of patients by randomised treatment group will be presented. The primary outcome, red cell transfusion outcomes, and healthcare associated infections will be analysed as described above in this dataset.

29. Harms

Safety outcomes and adverse events will be reported by treatment group.

30. Statistical Software and code

Stata v19 or later will be used (StataCorp. Stata Statistical Software: Release 19. College Station, TX: StataCorp LLC); or R v 4.4.1 or later. Any user-written R packages used will be referenced.

The following code will be applied for the analysis of primary and secondary outcomes:

Primary outcome and binary secondary outcomes:

```
xi: gllamm outcome i.TreatmentGroup i.diabetes, i(site) fam(binomial)
link(log)
```

Primary outcome and binary secondary outcome backup code:

```
binreg outcome i.TreatmentGroup i.diabetes, rr cluster(site)
```

DAH30:

```
qreg2 outcome i.TreatmentGroup i.diabetes, cluster(site)
qreg2 outcome i.TreatmentGroup i.diabetes, cluster(site)
```

Continuous outcomes:

mixed outcome i.TreatmentGroup i.diabetes || site: , reml

31. Modifications from the analysis outlined in the protocol

- 1. Estimand for the primary outcome has been defined.
- 2. That random effects for site will be included in regression models for the binary outcomes was clarified
- 3. The list of subgroups for subgroup analysis clarified as being those listed in Section 7.3 of the protocol
- 4. That the lower quartiles of DAH-30 will be compared has been stated.

32. References

- 2. GlobalSurg C. Surgical site infection after gastrointestinal surgery in high-income, middle-income, and low-income countries: a prospective, international, multicentre cohort study. *Lancet Infect Dis* 2018.

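### The SAP adjusts two interim looks by O'Brien-Fleming but sets every test at 5%, with no exception or final level for the primary test

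*SAP*

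**What the plan says.** - Section 13 (interim analyses): "Interim analyses will consider the defined study and safety endpoints", and these take place "after enrolment of 50% and 75% of patients, adjusted according to the O'Brien and Fleming method". The results go to the DSMC. The section gives no boundary values, spending function or final critical value.
- Section 14 (significance level): "All applicable statistical tests will be 2-sided and will be performed using a 5% significance level".
- Section 15, whose heading asks how type I error is controlled: "No adjustment for multiplicity is planned".
- Section 16 (intervals): "All confidence intervals will be two-sided 95% confidence intervals".
- Section 11 (sample size): "Assuming an incidence of 12%, and using a type I error of 0.05, we require 1,484 per group". The calculation makes no visible allowance for interim looks.

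Section 17 opens by allowing for exceptions stated elsewhere. Sections 14 to 16 contain no such clause.

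**The concern.** Surgical site infection is a study endpoint, so under Section 13 the primary outcome can be examined three times. O'Brien-Fleming is a joint set of boundaries. It holds the overall error at 5% only if the final critical value is raised along with the interim ones. Read literally, Sections 14 to 16 give the final primary test the full 5% after some of that error has already been spent.

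The decision rule for the main confirmatory test is therefore not settled. For a final p-value just under 0.05, the trial could be declared positive under one section and not under another, and a 95% interval could exclude 1 when the O'Brien-Fleming boundary has not been crossed. This should be settled before unblinding.

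**Working it through.** **Inputs.** Looks at 50%, 75% and 100% (Section 13), two-sided 5% (Section 14), and 12% vs 8.4% with 1,484 per group and 3,300 planned (Section 11). Assumptions: equal groups, so 3,300 / 2 = 1,650 each; information proportional to enrolment, t = 0.50, 0.75, 1.00; interim boundaries used for efficacy on the primary outcome.

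**Step 1: reproduce the plan's sample size.** Pooled-variance formula for two proportions, no continuity correction, mean rate 0.102:

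n = [1.960 × √(2 × 0.102 × 0.898) + 1.282 × √(0.12 × 0.88 + 0.084 × 0.916)]² / 0.036²
= [1.960 × 0.4280 + 1.282 × 0.4273]² / 0.001296, which rounds up to 1,484 per group.

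The same method gives 94.3% power at 14% vs 9.8%, against the stated 94%. Both figures match a single analysis at the full 0.05.

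**Step 2: boundaries that hold the overall error at 5%.** The three z-statistics are jointly normal with correlation √(tᵢ/tⱼ) for tᵢ < tⱼ. Classical O'Brien-Fleming sets |Z| > C/√t, and solving for a total crossing probability of 0.05 gives C = 2.024. The alpha-spending row uses the O'Brien-Fleming-type function with 0.025 per side.

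| Boundary | z at 50%, 75%, 100% | nominal two-sided p |
|---|---|---|
| Classical | 2.863, 2.337, 2.024 | 0.0042, 0.0194, 0.0430 |
| Alpha spending | 2.963, 2.359, 2.014 | 0.0031, 0.0183, 0.0440 |

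**Step 3: same interims, final test at 1.96.** Probability of first crossing at each look under no effect:

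- Classical, as designed: 0.0042 + 0.0167 + 0.0291 = 0.0500. With 1.96 at the end: 0.0042 + 0.0167 + 0.0353 = 0.0562.
- Alpha spending, as designed: 0.0031 + 0.0162 + 0.0307 = 0.0500. With 1.96 at the end: 0.0554 in total.

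A simulation of 8 million draws gave 0.0561 for the classical case. A less common variant, which puts the whole two-sided 0.05 through one spending function, ends at p = 0.0411 and gives 0.0577. The final level depends on the variant, and the SAP names none.

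**Step 4: power once the final level is corrected.** Drift = 0.036 / √[(0.12 × 0.88 + 0.084 × 0.916) / n], which is 3.246 at 1,484 and 3.423 at 1,650 per group. Rejections at the interims are counted.

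| Per group | Single look at 0.05 | Classical | Alpha spending |
|---|---|---|---|
| 1,484 | 90.1% | 89.4% | 89.6% |
| 1,650 | 92.8% | 92.3% | 92.4% |

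The loss is about half a percentage point. Applying the fixed-sample formula at 0.0430 alone would give 88.8% and 91.8%, but that ignores interim rejections and overstates the cost.

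**The case against.** The strongest defence is that the sections can be reconciled. O'Brien-Fleming by definition includes a reduced final critical value, and the 5% in Section 14 can be read as the overall two-sided level, which that method preserves. On that reading the error is 5%. Section 15 may be aimed at multiple outcomes, since interim looks have their own section and a specific rule normally governs a general one. Section 13 also states no efficacy stopping rule: if the interims could not lead to rejection, a final test at 5% would not be inflated. The protocol is not shown and may give the boundaries.

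Much of this stands. A reader might infer that the design certainly exceeds 5%. The SAP does not support that, because the excess depends on how two sections are read. A reader might also apply Section 14 to the interims, testing at 1.96 on all three looks, which would give 9.7%. Section 13 rules that out by requiring adjusted interims.

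The defence does not remove the conflict in wording. Sections 14 and 16 say all, without exception, and Section 15 answers a question about type I error control without pointing to Section 13. If the overall-level reading is intended, the text still needs to say so. Very strict interim boundaries (|Z| > 3.29 at both looks) would make a final test at 1.96 nearly harmless, at 5.02%, but the SAP names O'Brien-Fleming.

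**Conclusion.** The concern holds as a conflict within the SAP over the primary decision rule, not as proof that the trial's error rate is above 5%. If the interims allow rejection for efficacy, information accrues in line with enrolment, and the final test is run at nominal 0.05, overall two-sided type I error is about 5.5% (alpha spending) to 5.6% (classical), an excess of roughly 0.5 to 0.6 percentage points. The conclusion would differ only for a final p-value between about 0.043 or 0.044 and 0.050. The treatment estimate, model and sample size are unaffected. It should still be corrected, because following Section 14 literally misses the plan's own 5% on its main test.

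**What to change.** - **Section 14:** state that 5% is the overall two-sided level for the primary outcome and that the final test uses the O'Brien-Fleming final level. Name the boundary or spending function. The level is about 0.0430 (classical) or 0.0440 (alpha spending), to be recomputed from the boundary and looks actually used.
- **Section 15:** limit the no-adjustment statement to multiple outcomes and cross-refer to Section 13 for repeated looks at the primary outcome.
- **Section 16:** either match the primary interval to the final level (1 − 0.0430 = 95.7%, or 1 − 0.0440 = 95.6%) or keep 95% and state that this interval is not the decision rule. Either convention is defensible.

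The cost is SAP wording and a slightly stricter final threshold. At 1,484 per group, power falls just below the nominal 90%, but the planned 3,300 patients keep it at about 92.3-92.4%, so the sample size need not change.

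### The incision-only analysis set also governs safety, so a participant whose pre-incision drug reaction stops the operation drops out of the between-arm comparison of anaphylactoid reactions

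*SAP*

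**What the plan says.** Section 17 (Analysis Populations and Estimand) sets the default: "Except where stated otherwise, all analyses will be conducted under the principle of modified intention-to-treat". Participants stay in their randomised groups, "but only those participants who underwent a surgical incision will be included in the analysis".

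The treatment description in Sections 8 and 17 places the bolus "before surgical incision, and then infusion at 0.05 ml/kg/h until end of surgery". Exposure therefore starts before the event that defines the analysis set.

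Section 23 defines the anaphylactoid safety outcome as "An anaphylactoid reaction following study drug administration", with no reference to incision or surgery. Section 24 covers the safety outcomes with the same models as the primary outcome, under the heading "Analysis of primary outcome, and binary secondary/safety outcomes". Section 29 (Harms) says only: "Safety outcomes and adverse events will be reported by treatment group". Section 21 states the follow-up duty as: "All participants who are enrolled and randomly assigned to a group, and undergo surgery, must be followed for the duration of the study".

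**The concern.** Incision is a sensible condition for surgical site infection, because without an incision there is no surgical site. It does not suit drug safety, because the drug has already been given. Whether an incision follows is a post-randomisation, post-exposure event that a reaction to the drug can itself determine.

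For anaphylactoid reactions, the outcome definition takes in a reaction between bolus and incision, while the population rule removes the participant if that reaction stops the operation. The cases removed would tend to be the most severe immediate ones. At stake is the reported frequency of a rare serious harm in each arm, where each case counts.

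**Working it through.** **Step 1: is there an exception for safety?** The SAP states no figure on this point, so the first check is textual. Section 17 applies unless another population is stated. The places where one could be stated are:

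| SAP section | Content | Exception for safety? |
|---|---|---|
| 21 Withdrawal/follow-up | Follow-up duty for those randomised who undergo surgery | No |
| 23 Outcome definitions | Five safety outcomes, no population named | No |
| 24 Analysis methods | Binary safety outcomes share the primary outcome's models | No |
| 28 Additional Analyses | As-treated and per protocol sets for the primary outcome and red cell transfusion only | No |
| 29 Harms | Reporting by treatment group | No |

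**Step 2: which safety outcomes are affected?**
- Anaphylactoid reactions are anchored to drug administration. For these, the population rule alone causes the exclusion.
- Thromboembolism, seizures and cardiovascular events are each defined up to 30 days after surgery. A participant who never had surgery has no starting point for that window, so changing the population alone would not bring these events in.
- Transfusion reactions have no particular link to the pre-incision bolus.

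**Step 3: direction of the error.** Let r1 and r0 be the true reaction risks on TxA and placebo, and c1 and c0 the probabilities that a reaction stops the operation before incision. For rare events, the risk seen among incised participants is about r × (1 − c). Then:
- observed risk ratio ≈ (r1/r0) × (1 − c1)/(1 − c0)
- observed risk difference ≈ r1(1 − c1) − r0(1 − c0), which with equal c is (r1 − r0)(1 − c)

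With equal c the risk ratio is unchanged, while the absolute risks and the risk difference shrink by the factor (1 − c).

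**Step 4: illustrations.** All event counts and rates here are assumed. Arm size is 3,300/2 = 1,650, from the planned enrolment with equal allocation assumed.

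*Equal cancellation, c = 0.5; true counts 4 vs 2, observed 2 vs 1.*
- Risk ratio: (4/1,650)/(2/1,650) = 2.0 becomes (2/1,648)/(1/1,649) = 2.0.
- Risk difference: 2/1,650 = 0.121% becomes 2/1,648 − 1/1,649 = 0.061%.
- Standard error of the log risk ratio, about √(1/a + 1/b): √(1/4 + 1/2) = 0.87 becomes √(1/2 + 1/1) = 1.22.

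*Unequal cancellation, c1 = 0.6 and c0 = 0; true counts 5 vs 1, observed 2 vs 1.*
- Risk ratio: 5.0 becomes 5.0 × 0.4/1 = 2.0.

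*Possible size.* Assumed reaction rates of 0.05% to 0.3% give 1,650 × 0.0005 = 0.8 to 1,650 × 0.003 = 5.0 events per arm. With an assumed 25% to 50% leading to cancellation, 0.8 × 0.25 = 0.2 to 5.0 × 0.5 = 2.5 events per arm are lost. The share lost simply restates the assumed cancellation probability and is not a finding about this trial.

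**The case against.** Several objections have force.

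- **Scope.** A reader might infer that all safety outcomes are distorted in the same way. The documents do not support this: three outcomes run from surgery and one from transfusion, so only the anaphylactoid outcome is excluded purely by the population rule. This objection stands.
- **Bias.** A reader might infer that the comparison is necessarily pulled toward no harm. Section 24 reports risk ratios and the trial is double-blind, so equal cancellation probabilities after a reaction are plausible, and the risk ratio is then about unchanged. An attenuated ratio needs an added assumption, such as more severe reactions on TxA. This also stands. It leaves the loss in absolute risk, risk difference and precision.
- **Size.** Nothing in the SAP gives the number affected. Nor would a significance test necessarily change: with 1,650 per arm, Fisher's two-sided p is about 0.12 for 4 vs 0 and 0.50 for 2 vs 0, non-significant either way. This stands too.
- **Capture elsewhere.** Section 29 carries no incision condition of its own, the flow diagram would show how many were not analysed, and the protocol (not shown) may define a safety set or collect these events. This stands only in part. A case may well appear in an adverse event listing, but Section 24 puts the binary safety outcomes under the primary outcome's analysis and Section 17 fixes the population for it. The SAP refers to no separate safety set.

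**Conclusion.** The point holds as a defect in the safety population. Followed as written, the SAP leaves a dosed participant whose reaction prevents incision out of the between-arm comparison of anaphylactoid reactions, so inclusion can depend on the outcome. Absolute risk and the risk difference are understated, and precision is lost on a rare serious harm. The risk ratio is biased only if cancellation after a reaction differs by arm, which the documents do not indicate.

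The number affected is probably a handful and cannot be estimated from the SAP. The primary outcome and its analysis are untouched. Severity is moderate: worth correcting before unblinding, so that handling of any such case is not decided after the fact, but not a must-fix.

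**What to change.** 1. In Section 17, and again in Section 29, state that safety outcomes and adverse events are analysed by randomised group in all randomised participants who received any study drug, whether or not an incision was made. Keep modified intention-to-treat for the efficacy outcomes.
2. In Section 23, for participants dosed but not incised, start the 30-day safety windows at study drug administration. Without this, they would enter the denominators of outcomes whose window never opens for them.
3. In Section 29, report by arm the number dosed but not incised, with all their recorded events.

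The cost is a few sentences of SAP wording and one extra analysis flag. The downside is a few added participants whose day-30 data may be incomplete, since Section 21 requires follow-up only of those who undergo surgery. Sample size and efficacy analyses do not change.
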